## **2 STATISTICAL HYPOTHESES**

No formal statistical hypothesis testing is planned in this study.

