An internal Safety Monitoring Committee (SMC) will regularly review (approximately every 3 months, with the option to adapt the frequency based on recruitment rates) the available blinded safety data.

In addition, a Program Independent data monitoring committee (PiDMC) is in place to evaluate data over the entire rozanolixizumab clinical development program as this molecule is being investigated in several indications.

Number of study participants

In total and allowing for a dropout rate of 25%, approximately 60 study participants are planned to be enrolled and randomized in the study at up to 8 centers from the UK, with a target of 48 evaluable study participants completing the study. Evaluable study participants are those with BPI-SF scores at Baseline, Visit 15, and Visit 27 (see also Section 9.3).

[figure not shown]
Treatment groups and duration

The maximum study duration per study participant will be 37 weeks.

- Screening Period: Eligibility will be assessed during the Screening Period of up to 28 days.
- Run-in Period: Study participants who have been confirmed eligible to participate in the study will be randomized 1:1:1 to receive rozanolixizumab 560mg sc QW or placebo sc QW, as described in the study design section above. During the 2-week Run-in Period, all study participants will receive placebo sc QW and will be blinded to this treatment.
- Treatment Period: As shown in Section 1.2, study participants will receive rozanolixizumab 560mg sc QW for two 12-week Treatment Periods, placebo sc QW for the first 12-week Treatment Period followed by rozanolixizumab 560mg sc QW for the second 12-week Treatment Period, or placebo sc QW for two 12-week Treatment Periods.
- Run-out Period: At the end of both 12-week Treatment Periods, all study participants will receive placebo sc QW during a 2-week Run-out Period and will be blinded to this treatment.
- Safety Follow-up Period: Study participants who complete both Treatment Periods and Run-out Period will enter the 5-week SFU Period. These participants will attend the EOT visit 2 weeks after the last dose in the Run-out Period and the SFU/EOS visit 4 weeks later (6 weeks after the last dose in the Run-out Period). Study participants who permanently discontinue IMP are encouraged to complete the EOT/EW Visit and the SFU/End of Study (EOS) Visit.

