## 1 INTRODUCTION

The purpose of this Statistical Analysis Plan (SAP) is to provide all information that is necessary to perform the required statistical analysis of study FM0001. The SAP summarizes what will be provided in the tables, figures and listings (TFLs) to be included in the final clinical study report (CSR) according to the protocol, as well as defining the output to be generated for safety signal detection (SSD) and for the Early Readout Analysis. The TFL specifications are contained in a separate document and are based on the UCB Standard TFL Shells. The requirements for the Early Readout Analysis will be defined in the Unbinding Plan and the Safety Monitoring Committee (SMC) procedures will be defined in a separate charter.

Unless specified in the sections below, the study will be analyzed as described in the most recent version of the protocol. If a future protocol amendment necessitates a substantial change to the statistical analysis of the study data, this SAP will be amended accordingly. In addition, if the methodology for the analysis of primary or secondary endpoints must be modified or updated prior to unblinding, a SAP amendment will be required. If, after unblinding, additional analyses are required to supplement the planned analyses described in this SAP, these changes will be described in the CSR together with the associated rationale. Other minor changes to non-key analyses will also be documented in the CSR.

The content of this SAP is compatible with the International Council for Harmonisation (ICH)/Food and Drug Administration (FDA) E9 Guidance documents (Phillips et al, 2003).

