## **3 SAMPLE SIZE DETERMINATION**

The operating characteristics of the design were evaluated using a simulation approach and based on estimates of variability and treatment effects from fibromyalgia studies reported in clinicaltrials.gov and other papers. BPI-SF was used consistently in duloxetine studies. A sample size of 48 completed study participants gives more than 80% probability that if the true difference of the mean BPI-SF interference score after 12 weeks of treatment on rozanolixizumab compared with placebo was 1.0 units or better, then the comparison would pass a 1-sided 10% significance test. This assumes a between-study participant standard deviation component for the BPI-SF interference score of 1.74 units, and a within-study participant SD of 1.5 units (a total between-study participant SD of 2.3 units) after accounting for the Baseline BPI-SF interference score. Through simulations of the design, it was estimated that 60 study participants starting the study would achieve the desired power, assuming a drop-out rate of 25%, and assuming a uniform distribution of drop-out timings. This accounts for the fact that drop-out participants contribute partial information up to the point of discontinuation and corresponds to an effective sample size of 48.

Simulations including the interim analysis were also conducted, and based on the impact on the operating characteristics, it was decided that no multiplicity adjustment was needed for the final analysis.

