### 5.8.2.1 Primary Analysis of Primary Efficacy Variables(s)

The LMM for the BPI-SF interference score will have treatment as a fixed effect and the study participant ID will be included as a random effect.

The following additional fixed effects will be included:

- Treatment Period (1 or 2)
- assessment number within the period (1st, 2nd, or 3rd assessment categorical) number corresponding to Visit 7, 11, and 15 for Treatment Period 1, or Visit 19, 23, or 27 for Treatment Period 2)

- an interaction of treatment by assessment number
- an interaction of assessment number-by-Treatment Period

The following covariates will also be included:

- BPI-SF interference scores at Baseline (taken at Visit 3, prior to dosing)

The model can also be written as follows:

$$Y_{ij} = Y_{i,bl} + \text{Period}_{ij} + \text{Assessment}_{ij} + \text{TRT} + \text{Assessment}_{ij} \times \text{TRT}_{ij} + \text{Period}_{ij} \times \text{Assessment}_{ij} + (1|s_i)$$

Where  $Y$  indicates the measurement of interest (BPI-SF interference score in this case),  $i$  the  $i$ -th participant,  $j$  the  $j$ -th observation for each participant,  $\times$  indicate an interaction, and  $(1|s_i)$  indicate the random intercept effect for participant  $i$ .  $Y_{i,bl}$  indicates the baseline value for participant  $i$ . Note that this model is specified as-is for conceptual clarity, but is over-parameterized, which may need to be taken into account during model fitting.

The model will utilize an unstructured covariance pattern for the repeated measures. If the model does not converge using the unstructured pattern, then an autoregressive covariance structure will be used. The Kenward-Roger approximation will be used to estimate the denominator degrees of freedom.

The LS Means estimate for each of the treatments with 95% CI should be reported. LS Means should be estimated assuming assessment effects of assessment 3 and using the period effect for period 2. In addition, the LS Means estimate of the differences between rozanolixizumab 12 weeks and 24 weeks, respectively, and placebo should be reported, using the same period and assessment effects as before.

- Rozanolixizumab 12 weeks – Placebo
- Rozanolixizumab 24 weeks – Placebo
- Rozanolixizumab 12 weeks- Rozanolixizumab 24 weeks

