P-values for the baseline, treatment period, assessment number, treatment by assessment number, and treatment period by assessment number interaction terms will be reported.

All study participants in the FAS with Baseline BPI-SF score and one or more post-Baseline assessments will be included in the model.

Inter current event (ICE): Permanent discontinuation of treatment will be handled using a hypothetical strategy assuming that the study participants did not experience the events, with data following discontinuation excluded from analysis.

In addition, summary statistics of all results at assessment number 3 (in Treatment Periods 1 and 2) for all participants included in the model will be reported in the primary efficacy table by treatment group.

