### 5.8.2.2 Secondary Analysis of Primary Efficacy Variable(s)

As secondary analysis strategy, each period will be analyzed separately using a mixed effect model, with study participant as random effect and treatment, assessment number, treatment by

assessment number interaction, and Baseline as fixed effects. For Treatment Period 1, there will be 2 treatment groups: placebo and rozanolixizumab. For Treatment Period 2, there will be 3 as defined for the primary analysis.

The LS Means estimate for each of the treatments with 95% CI should be reported, as well as the LS Means estimate of the differences between relevant treatment groups. See below treatment differences to be estimated at by period analysis.

Treatment Period 1;

- Rozanolixizumab 12 weeks – Placebo 12 weeks\_Seq2 (between Seq1 and Seq2)
- Rozanolixizumab 12 weeks – Placebo 12 weeks\_Seq3 (between Seq1 and Seq3)
- Rozanolixizumab 12 weeks – Placebo 12 weeks (between Seq1 and pooled placebo from Seq2 and Seq3)

Treatment Period 2;

- Rozanolixizumab 24 weeks – Placebo 24 weeks (between Seq1 and Seq3)
- Rozanolixizumab 12 weeks - Rozanolixizumab 24 weeks (between Seq2 and Seq1)
- Rozanolixizumab 12 weeks – Placebo (between Seq2 and Seq3)

P-values for the baseline, assessment number, and treatment by assessment number interaction should also be reported.

In addition, summary statistics of all results at assessment number 3 (in Treatment Period 1 and 2, as appropriate) for all participants included in the model will be reported in the secondary analysis summary tables.

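### Does the unstated interval level for the primary treatment difference leave the 1-sided 10% sizing criterion without a result to match it?

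*SAP*

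**What the plan says.** SAP 2 is one sentence: "No formal statistical hypothesis testing is planned in this study". SAP 3, like protocol 9.8, justifies the sample size by the probability that, if the true difference is 1.0 unit or better, "then the comparison would pass a 1-sided 10% significance test".

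The reporting instructions in SAP 5.8.2.1 come in three parts:

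- For treatment means: "The LS Means estimate for each of the treatments with 95% CI should be reported".
- For contrasts: "the LS Means estimate of the differences between rozanolixizumab 12 weeks and 24 weeks, respectively, and placebo should be reported". No interval or level is named.
- For tests: "P-values for the baseline, treatment period, assessment number, treatment by assessment number, and treatment period by assessment number interaction terms will be reported". The rozanolixizumab 12 weeks minus placebo contrast is not on this list.

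SAP 5.8.2.2 (the by-period analysis) puts the means and the contrasts in one sentence. It asks for LS means with 95% intervals, "as well as the LS Means estimate of the differences between relevant treatment groups".

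SAP 1 says the document's purpose is to "provide all information that is necessary to perform the required statistical analysis of study FM0001". The same paragraph places the table specifications in a separate document, and SAP 5.1 leaves the details of tabulations to the shells.

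On numbers, protocol 1.1 pairs about 60 randomised and 25% dropout "with a target of 48 evaluable study participants completing the study". Protocol 4.1 and SAP 1.2 say the same without the word evaluable. SAP 3 describes 48 as an effective sample size that credits partial data from participants who drop out.

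**The concern.** SAP 5.8.2 names rozanolixizumab for up to 12 weeks versus placebo as the main difference of interest. Read literally, the SAP asks only for a point estimate of it. The treatment-by-assessment p-value is an interaction test and does not stand in for this contrast. The one efficacy benchmark in the SAP, the 1-sided 10% criterion, then has no listed output. The posterior-probability thresholds in protocol 9.7.1 belonged to the interim analysis, which SAP Amendment 1 removed.

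Two consequences would follow if this were a real gap. The level could be settled after the Early Readout (SAP 5.12.1) has unblinded the study team. And a reader who took a 95% interval excluding zero as success would apply a stricter standard than the one behind the power statement.

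The head count also looks wrong: 25% dropout from 60 leaves 45, not 48.

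**Working it through.** **Inputs.** SAP 3: true difference 1.0; between-participant SD 1.74; within-participant SD 1.5; 1-sided 10%; 60 randomised; 25% dropout, uniform in time. SAP 1.2: 1:1:1 allocation to three sequences. SAP 5.8.2.1: six post-baseline assessments, three per period; effects for period, assessment, treatment and the two interactions; contrast at assessment 3.

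**Total SD.** sqrt(1.74² + 1.5²) = 2.297, matching the stated 2.3.

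**Power.** Take V = 1.5² I + 1.74² J for each participant (I the identity matrix, J all ones). Information is the sum over participants of X'V⁻¹X. The SE is the square root of the diagonal element of its inverse for rozanolixizumab 12 weeks versus placebo at assessment 3. Power = Φ(1.0/SE − 1.2816).

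| Scenario | SE | Power, 1-sided 10% |
|---|---|---|
| 48 completers (16 per sequence) | 0.4413 | Φ(2.266 − 1.282) = 83.8% |
| 60 randomised, 25% uniform dropout before Visit 27 | 0.4366 | Φ(2.290 − 1.282) = 84.3% |
| 45 completers, no partial data | 0.4557 | Φ(2.194 − 1.282) = 81.9% |

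The stated figure of more than 80% reproduces in all three. With only the end-of-period values (two per participant), 48 completers give SE 0.483 and 78.4%. The claim therefore relies on the longitudinal model, which is the one the SAP specifies.

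**Effective sample size.** 48 x (0.4413/0.4366)² = about 49, close to the 48 in SAP 3.

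**Interval for the contrast.** A 1-sided 10% test corresponds to a two-sided 80% interval. With 48 completers:

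- 95%: 1.96 x 0.4413 = 0.865 (about 0.86)
- 80%: 1.2816 x 0.4413 = 0.566 (about 0.57)

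The second follows from the first: 0.865 x 1.2816/1.96 = 0.566. With Kenward-Roger degrees of freedom the same conversion uses t quantiles. The level changes neither the estimate nor its SE.

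**Levels named in the SAP.** Geometric means of concentrations (5.1), forest plots of change from baseline (5.8) and treatment LS means (5.8.2.1 and 5.8.2.2) all use 95%. No other confidence level appears.

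**Head count.** Protocol 4.4 counts a participant as completing only after safety follow-up, so 60 x 0.75 = 45. Protocol 1.1 defines evaluable differently: scores at Baseline, Visit 15 and Visit 27. SAP 3 does not give the window over which dropout is uniform. The range under three assumed windows is:

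- All dropout before Visit 27: 45 evaluable.
- Day −14 to Day 218: 182 of 231 days precede Day 169, so 60 x (1 − 0.25 x 182/231) = 48.2.
- Day 1 to Day 218: 60 x (1 − 0.25 x 168/217) = 48.4.

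So 48 evaluable can be right as written. The strict mismatch is with completing the study.

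**The case for a change.** The strongest case for a change is that this is the trial's headline number and the remedy is one line. SAP 1 claims to contain everything needed, the general rules in SAP 5.1 set no default confidence level for model estimates, and the shells were not available to check. The choice of level also affects how a result reads. At a true difference of 1.0, a 95% interval would exclude zero with probability about 62% (48 completers) to 63% (60 randomised with dropout), against about 84% for the sizing criterion.

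The textual observation stands: no level is written next to the differences. The rest does not carry far. The 62% to 63% measures success under a rule the plan never declares, so it is not a loss of power. SAP 5.8.2.2 joins means and differences in one sentence and SAP 5.8.2.1 puts them in consecutive ones, so carrying 95% across is the natural reading. Settling the level late would gain nobody anything, because no final decision hangs on it and any level can be recovered from the reported SE and degrees of freedom. SAP 1 also requires analyses added after unblinding to be described in the study report with a rationale.

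On the count, 45 is correct for study completion. Substituting it for 48 evaluable could replace a defensible figure with a different quantity.

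**Conclusion.** No change to the plan follows. SAP 2 and SAP 3 do not conflict: one declines formal testing, and the other describes the design's operating characteristics against a nominal criterion. The sizing is sound, with power about 84% against a stated figure above 80%. The missing level is a detail that analysts would fill with the 95% used elsewhere in the SAP. The 80% interval matching the sizing criterion (half-width about 0.57) can be derived from the same output.

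The phrase about 48 completing is clerical. Strictly, about 45 are expected to complete the study and 48 is the effective sample size. Neither the power nor any analysis set depends on that head count.

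The figures assume compound symmetry from the two stated SDs and normal quantiles, whereas SAP 5.8.2.1 plans an unstructured covariance with Kenward-Roger degrees of freedom. The SEs could shift somewhat under that model, but the reasoning about the interval level would not.

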## **3 SAMPLE SIZE DETERMINATION**

The operating characteristics of the design were evaluated using a simulation approach and based on estimates of variability and treatment effects from fibromyalgia studies reported in clinicaltrials.gov and other papers. BPI-SF was used consistently in duloxetine studies. A sample size of 48 completed study participants gives more than 80% probability that if the true difference of the mean BPI-SF interference score after 12 weeks of treatment on rozanolixizumab compared with placebo was 1.0 units or better, then the comparison would pass a 1-sided 10% significance test. This assumes a between-study participant standard deviation component for the BPI-SF interference score of 1.74 units, and a within-study participant SD of 1.5 units (a total between-study participant SD of 2.3 units) after accounting for the Baseline BPI-SF interference score. Through simulations of the design, it was estimated that 60 study participants starting the study would achieve the desired power, assuming a drop-out rate of 25%, and assuming a uniform distribution of drop-out timings. This accounts for the fact that drop-out participants contribute partial information up to the point of discontinuation and corresponds to an effective sample size of 48.

Simulations including the interim analysis were also conducted, and based on the impact on the operating characteristics, it was decided that no multiplicity adjustment was needed for the final analysis.

## **4 POPULATIONS FOR ANALYSIS**

### **All Study Participants Set:**

The All Study Participants Set (ASP) consists of all study participants that sign the informed consent form. This set includes screening failures.

### **Randomized Set:**

The Randomized Set (RS) will consist of all participants randomized into the study.

### **Safety Set –as Randomized:**

The Safety Set as randomized (SS-r) consists of all study participants who received any study treatment, including during the Run-In period. The study participants will be analyzed according to the randomized treatment groups during the specific treatment period.

The SS-r will be used for production of safety analysis by visit and demographic and immunogenicity analysis.

### **Safety Set – as Treated:**

The Safety Set as treated (SS-t) consists of all study participants who received any study treatment, including during the Run-In period.

For analysis purposes, the SS-t is used only for tabulating AEs, as described in [Section 5.6.25.6.2](#).

### **Full Analysis Set:**

The Full Analysis Set (FAS) consists of all study participants in the SS-r who have a Baseline value and at least one post-Baseline efficacy endpoint assessment. Study participants who receive at least one dose of treatment not per randomization schedule will be excluded from the FAS.

This analysis set will be used for the summaries and analyses of primary, secondary, and exploratory efficacy variables data.

### **Pharmacokinetic Set:**

The Pharmacokinetics Set (PKS) consists of all study participants in the SS-r who have at least one dose of active IMP and at least one measurable PK concentration, including below limit of quantification (BLQ) samples. The PKS will be used for all PK summaries and analyses. If a study participant in the PKS is missing individual time points or are otherwise unobservable, they will be included in the PKS but those time points will be omitted from the PK summaries, as appropriate.

### **Pharmacodynamic Set:**

Pharmacodynamic set (PDS) is a subset of the FAS, consisting of those study participants who had no important protocol deviations affecting the PD variables, (as confirmed during a pre-analysis review of the data prior to unblinding), and who had at least one valid post-Baseline measurement of serum total IgG or IgG subclasses. The final PDS will be identified after unblinding to confirm availability of at least one post-baseline valid measurement due to blinding. PDS will be used for all PD summaries and analyses.

Participants who had important protocol deviations affecting the relevant efficacy/PK/PD variables, as confirmed during a pre-analysis review of the data prior to unblinding may be excluded from relevant analyses. Such exclusions will be agreed and documented prior to unblinding and will be described in TFLs and/or the CSR.

## 5 STATISTICAL ANALYSES

### 5.1 General Considerations

All tables, figures, and listings (TFLs), including statistical evaluation, will be produced by Veramed using SAS version 9.4 or higher (SAS Institute, Cary, North Carolina, USA). Analysis data will adhere to Clinical Data Interchange Standards Consortium (CDISC) guidance documents for Analysis Data Model (ADaM) and follow the UCB interpretation.

Listings will be presented by study participant and planned treatment sequence. The presentation of tables and figures varies from variable to variable and will be specified in the respective section.

All tabulations will be performed per specified analysis set, visit and time point (where applicable). Details of planned tabulations will be described in the TFL shells. Data listings containing all documented data and all derived data will be generated.

#### 1) Categorical Variables

Categorical variables will be summarized using frequency counts and percentages. Unless otherwise stated, the denominator for the percentage calculations will be based on the number of study participants in the respective analysis set, treatment sequence, treatment group, visit and time point (as applicable) with non-missing data. If there are any study participants with missing values for a categorical variable, an additional row displaying the number of study participants with missing data will be added.

#### 2) Continuous Variables

Summary statistics will be presented for continuous variables including number of participants (n), mean, standard deviation (SD), median, minimum and maximum. Geometric mean (geoMean), geometric coefficient of variation (geoCV) and 95% CI for the geoMean will also be presented in the summaries of PK concentration data. The 25th and 75th percentiles (Q1 and Q3) will be included for descriptive statistics of ePRO data.

When reporting descriptive statistics, the following rules will apply:

- Mean (arithmetic and geometric), SD, Q1, Q3, and median will use 1 decimal place more, or 1 significant figure more than the original data
- Confidence intervals will use 1 decimal place more, or 1 significant figure more – depending on the reporting format of the original data – than the value around which the confidence interval is constructed
- Coefficient of variation (CV) will be reported as a percentage to 1 decimal place
- Minimum and maximum will be reported using the same number of decimal places or significant figures as the original value
- If no participants have data at a given time point, then only n=0 will be presented. If n<3, then only the n, minimum and maximum will be presented. If n=3, then only n, minimum, mean, median and maximum will be presented. The other descriptive statistics will be left blank.

